## **11. Parameters to be Measured:**

- Age
- PSA levels
- Subjective findings of rectal examination
- Post-procedure complications
- Anxiety and stress scores (STAI-I and II, pre-op and post-op)
- Pain scores (VAS)

---

## **12. Where and by Whom Parameters Will Be Collected:**

All patients will be recruited from the Urology outpatient clinics of Etlik City Hospital. Assessments will be carried out by Clinical Urology Physicians.

---

## **13. Routine vs. Study-Specific Parameters:**

All parameters are part of routine clinical evaluations for patients with high PSA. No study-specific laboratory or additional tests will be requested.

---

## **14. Estimated Study Duration:**

- Start: 10.12.2023
- End of patient recruitment: 30.12.2024
- 12 months of data collection, 5 months for manuscript preparation and submission
- Total: 17 months

---

## **15. Study Endpoint:**

- The study will conclude on 20.05.2025

---

## **16. Criteria for Termination:**

- Data collection will end once sufficient data is collected.

---

## **17. Outcome Evaluation:**

The primary endpoint is the tabulation and statistical analysis of STAI responses before and after the procedure among different groups. The secondary endpoint is the writing and publication of the study results.

---

Previous literature has shown that prostate biopsy induces anxiety and depression. Zisman et al., in a prospective study of 211 men, found that 64% experienced decreased well-being and anxiety from the pre-biopsy period up to 30 days after. Fowler et al. showed that anxiety may persist for up to 12 months, even in patients with negative biopsy results. Our study seeks to answer whether pre-procedural videos intensify the anxiety already known to be associated with the biopsy.

---

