**1. Full Title of the Study:**

**"A Prospective Comparative Study of the Effect of Video Education on Pain and Anxiety in Patients Undergoing TRUS-Guided Prostate Biopsy"**

---

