**2. Purpose and Significance of the Study:**

The widespread use of PSA (Prostate-Specific Antigen) has facilitated the early detection of prostate cancer. Biopsies are performed on patients who are suspected to have prostate cancer based on elevated PSA and digital rectal examination. Transrectal ultrasound-guided prostate biopsy is the standard diagnostic procedure. The increasing use of PSA has led to a rise in the number of biopsies.

It has been reported that prostate biopsies and the diagnosis of prostate cancer cause anxiety in men. These procedures may lead to pain, anxiety, and stress.

Today, patients frequently use the internet to gather information. Watching videos of procedures before surgery via digital platforms is common. This study aims to measure the effect of watching TRUS-BX videos before and after the procedure on patients' anxiety and stress levels.

---

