#### **4. Study Design:**

This is a comparative study of anxiety scores and visual analog scale (VAS) pain scores before and after the procedure. All patients are informed in the outpatient clinic about the TRUS-BX procedure after elevated PSA is detected.

The study was reviewed and finalized with the contributions of [name] [name] from the Psychiatry Department of Ankara Etilik City Hospital.

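### Publication is named as the secondary endpoint, so pain, which is in the title and measured in every group, has no endpoint and no fixed VAS variable

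*Combined protocol and SAP*

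**What the plan says.** Section 17 of the combined protocol and SAP names two endpoints. The first is STAI: "The primary endpoint is the tabulation and statistical analysis of STAI responses before and after the procedure among different groups". The second is: "The secondary endpoint is the writing and publication of the study results".

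Pain appears elsewhere in the same document:

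- **Section 1 (title):** the study concerns the "Effect of Video Education on Pain and Anxiety".
- **Section 4 (design):** it is a "comparative study of anxiety scores and visual analog scale (VAS) pain scores before and after the procedure". The schedules for the control, video and image groups each place one VAS before the procedure and one after biopsy.
- **Section 11:** VAS pain is on the list of parameters to be measured.

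The aim in Section 2 leaves pain out. It is to "measure the effect of watching TRUS-BX videos before and after the procedure on patients' anxiety and stress levels". The closing question of Section 17 is likewise about anxiety only.

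Section 18 lists parametric and non-parametric methods, linear regression among them, without tying any to a variable. The closing Statistical Analysis text gives ANOVA or Kruskal-Wallis for group comparisons, Bonferroni-corrected Mann-Whitney tests afterwards and a 0.05 threshold, again with no outcome named.

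**The concern.** A secondary endpoint should be something measured in patients. Here that place is taken by a dissemination milestone, and the one other outcome that the title promises is left without a status. This is a stated entry that is wrong, not merely a missing detail.

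The practical consequence is freedom of choice. With VAS recorded twice, the pain result could be the post-procedure score or the change from the pre-procedure score, and either could be presented as the pain result once the data are known. The two need not agree. The pre-procedure score is taken before any biopsy pain, is cut off below 5 by Section 9, and is read there as a sign of anxiety-stress disorder. A change score subtracts that doubtful quantity in full. A pain claim from such an analysis would carry more than the nominal error rate and no agreed rank beside STAI.

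**Working it through.** **1. Where pain stands, section by section**

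| Place | Pain included? | What it fixes |
|---|---|---|
| Section 1, title | Yes | Pain named beside anxiety |
| Section 2, aim | No | Anxiety and stress only |
| Section 4, design and group schedules | Yes | VAS before and after, same two occasions in all groups |
| Section 11, parameters | Yes | Collection only |
| Section 17, primary endpoint | No | STAI |
| Section 17, secondary endpoint | No | Publication |
| Section 18 and closing Statistical Analysis text | Not named | General tests, no outcome variable |

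So the measurement occasions and a candidate test are given. The VAS variable, its endpoint status and its rank are not.

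**2. The plan's own figure**

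The plan gives no figure for pain: no VAS standard deviation, expected difference or power. Its only calculation is 26 per group (78 in total) for Cohen's f = 0.40, alpha 0.05 and power 80%, with no outcome named. A one-way ANOVA with those inputs needs 22 per group (66 in total, power 81.8%); 78 gives 88.3%. That difference is on the conservative side and does not bear on this point. The group size of 26 is used below.

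**3. Cost of leaving the VAS variable open**

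Inputs: three groups of 26 (Section 7); 0.05 threshold (closing Statistical Analysis text); no true effect; normal scores with equal variances before and after. The pre-post VAS correlation r is not in the documents, so it is assumed over 0 to 0.7. The cut-off at 5 is not modelled.

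The overlap between the two candidate outcomes is corr(post, change) = (1 − r) / √(2(1 − r)) = √((1 − r)/2).

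Each simulated trial was analysed by one-way ANOVA on post-procedure VAS and again on change, and counted as positive if either gave p < 0.05 (40,000 trials per row):

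| r | corr(post, change) | Post alone | Change alone | Either |
|---|---|---|---|---|
| 0 | 0.71 | 5.1% | 4.9% | 8.5% |
| 0.3 | 0.59 | 5.1% | 4.9% | 8.9% |
| 0.5 | 0.50 | 5.2% | 5.0% | 9.4% |
| 0.7 | 0.39 | 5.0% | 5.0% | 9.4% |

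The simulation error on the last column is about √(0.09 × 0.91 / 40,000) = 0.14 percentage points. For comparison, two independent tests would give 1 − 0.95² = 9.75%. The choice therefore takes the rate from 5% to about 9%.

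**4. Which form loses least**

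With equal variances σ² at both times, the outcome variance is σ² for the post score, 2σ²(1 − r) for change, and σ²(1 − r²) for the post score adjusted for the pre score. At r = 0.3 these are 1.00σ², 1.40σ² and 0.91σ². At r = 0.7 they are 1.00σ², 0.60σ² and 0.51σ². The adjusted form has the smallest variance in both cases. In every group VAS is listed before any video or drawing is shown, so the pre score cannot have been altered by the intervention and is a legitimate covariate.

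**The case against.** The best defence is that this is an anxiety study that also records pain. Section 2, the expected benefits in Section 3 and the closing question of Section 17 all concern anxiety or stress. This stands. A reader might infer from the title that half of the study's question goes untested, but the documents do not support that: the aim never includes pain. The fault is a conflict between the title and design on one side and the aim and endpoints on the other.

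A reader might also infer that there is no way of comparing pain at all. That goes too far. The closing Statistical Analysis text is not limited to STAI, and its three-group test, post-hoc correction and threshold could be applied to VAS. What stands is narrower: a test without a named variable and rank is not a pre-specified comparison.

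It is tempting, too, to count VAS as one more test on top of three STAI tests (before, after, change) and to quote a rise in the overall false-positive rate from about 12% to about 17%. Section 17 does not list those three tests, the 12% is a separate matter of STAI multiplicity, and the upper figure runs from about 14.5% to 17% with the assumed VAS-STAI correlation. It does not measure the choice between two VAS outcomes and should not be used here.

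Finally, it may seem inconsistent to distrust the pre-procedure VAS in a change score and then adjust for it. The difference is that a change score fixes its weight at one, whereas the linear model estimates the weight and lets it fall towards zero if the pre score says little about biopsy pain. Unadjusted post-procedure VAS would also be acceptable if fixed in advance.

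**Conclusion.** The point holds as a defect of endpoint definition that should be corrected. Section 17 gives the secondary place to publication. Pain, although in the title and design and measured in every group, has no endpoint, no chosen VAS variable and no rank. None of this depends on a calculation.

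The size, 5% rising to about 9% for a pain claim, is illustrative. It assumes that exactly the two VAS outcomes are tried, that the more favourable is reported, that scores are roughly normal and that the pre-post correlation lies between 0 and 0.7. The STAI question and the data collected are unaffected. Power for pain cannot be worked out from the documents.

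**What to change.** **Section 17.** Replace the secondary endpoint with: *post-procedure VAS pain score, compared among the three groups with adjustment for pre-procedure VAS, ranked below the primary STAI endpoint.* Move publication to the timeline text in Section 14.

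**Section 18 and the closing Statistical Analysis text.** Name the model for VAS: a linear model of post-procedure VAS on group and pre-procedure VAS. Linear regression is already on the Section 18 list, but the closing text offers only ANOVA or Kruskal-Wallis, so a change in Section 17 alone would leave the two in conflict.

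Section 17 speaks only of STAI responses and defines no single primary comparison. The ranking can be written now but has full force only once one is named.

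**Cost.** A few sentences and a slightly longer analysis. VAS is already collected in every group, so no patients, visits or new sample size are needed for a secondary endpoint. If analysis has already begun, label pain as exploratory and report it as such.

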## **18. Statistical Analysis:**

Both parametric tests (t-test, ANOVA, Pearson correlation, linear regression) and non-parametric tests (Wilcoxon, Mann-Whitney U, Kruskal-Wallis, Friedman, Spearman correlation) will be used.

Descriptive statistical analyses will be performed using SPSS software (version 20, SPSS Inc., Chicago, USA).

---

### **Name / Signature**

**Principal Investigator:**  
**[name]**

### **Statistical Analysis**

All statistical analyses were performed using SPSS software [insert version]. Continuous variables were expressed as mean  $\pm$  standard deviation, and categorical data as frequencies and percentages. Group comparisons were made using the Kruskal-Wallis test for non-parametric data and ANOVA for normally distributed data. Post-hoc pairwise comparisons were conducted using the Mann-Whitney U test with Bonferroni correction. A p-value  $<0.05$  was considered statistically significant. A priori power analysis was conducted using G\*Power

software version 3.1.9.7 to determine the adequate sample size. Assuming an alpha ( $\alpha$ ) level of 0.05 and a beta ( $\beta$ ) level of 0.20 (power of 80%), and an effect size (Cohen's  $f$ ) of 0.40, it was calculated that approximately 26 participants per group (78 in total) would be required to detect meaningful differences between the three groups.

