#### **Control Group:**

Patients are given verbal information about the procedure. Then:

- VAS test is applied.
- STAI-II (Trait Anxiety) and STAI-I (State Anxiety) scales are administered pre-procedure.
- After biopsy: VAS and STAI-I are re-administered.
- No visual material is shown.

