#### **Video Group:**

Patients are given verbal information. Then:

- VAS test is applied.
- Videos about the procedure are found and watched with the patients via digital video platforms.
- STAI-II and STAI-I are administered pre-procedure.
- After biopsy: VAS and STAI-I are re-administered.

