#### **Image Group:**

Patients are given verbal information. Then:

- VAS test is applied.
- Illustrated drawings (from books) about the procedure are shown to the patients.
- STAI-II and STAI-I are administered pre-procedure.
- After biopsy: VAS and STAI-I are re-administered.

---

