## **7. Sample Size:**

No similar study was found in the literature. There are three independent groups:

- Video group,
- No visual group,
- Image group.
- Assuming an alpha ( $\alpha$ ) level of 0.05 and a beta ( $\beta$ ) level of 0.20 (power of 80%), and an effect size (Cohen's  $f$ ) of 0.40, it was calculated that approximately 26 participants per group (78 in total) would be required to detect meaningful differences between the three groups.

---

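### Trait anxiety (STAI-II) is collected in every group but has no stated role in the group comparison, and as now timed it is not a clean covariate

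*Combined protocol and SAP*

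**What the plan says.** Section 4 gives STAI-II to everyone. In the control group it comes straight after the VAS test: "STAI-II (Trait Anxiety) and STAI-I (State Anxiety) scales are administered pre-procedure". In the video group a step comes in between, "Videos about the procedure are found and watched with the patients via digital video platforms", and only then "STAI-II and STAI-I are administered pre-procedure". The image group follows the same order, with "Illustrated drawings (from books) about the procedure are shown to the patients" before the questionnaires. After biopsy, all three groups repeat VAS and STAI-I only.

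Section 11 lists "Anxiety and stress scores (STAI-I and II, pre-op and post-op"), which can be read as a second STAI-II after biopsy. Section 4 does not schedule one.

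Section 17 makes the STAI responses before and after the procedure the primary endpoint. It does not say which scale is meant, or whether a level or a change is compared.

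For the analysis, the final Statistical Analysis text states "Group comparisons were made using the Kruskal-Wallis test for non-parametric data and ANOVA for normally distributed data", followed by Bonferroni-corrected Mann-Whitney tests. None of these, as written, includes a covariate. Section 18 lists linear regression and correlation without outcome, covariate or purpose. No method of allocating patients to groups is described.

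**The concern.** A trait score is an obvious covariate for a state score on the same instrument. Leaving it out has two costs if it predicts STAI-I. The trait-related variance stays in the error term, so intervals are wider than they need be. And, with no allocation method described, any trait difference between groups stays in the group effect. The study asks whether videos intensify anxiety, so a more anxiety-prone video group would mimic the finding being sought.

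The timing creates the opposite risk. STAI-II follows the material in two groups and follows no material in the third. If watching a video or seeing drawings changes how patients answer STAI-II, adjusting for it removes part of the effect or creates a false one. An analyst who simply put STAI-II into the regression that section 18 allows could make the comparison worse.

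**Working it through.** **Inputs from the documents:** three groups, alpha 0.05, power 80%, Cohen's f = 0.40, and "approximately 26 participants per group (78 in total) would be required".

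**Assumed:** the within-group trait-state correlation r (0.3, 0.5, 0.7), any trait imbalance, any shift s in STAI-II caused by the material, and the pre-post correlation c. Results are in SD units because no STAI standard deviation is given.

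**1. The plan's own figure.** One-way ANOVA, noncentral F with λ = N f² and df 2 and N − 3. At N = 78, λ = 78 × 0.16 = 12.48 and power is 88.3%. The smallest design reaching 80% is 22 per group (66 in total, 81.8%). So 26 per group does not reproduce from the stated inputs, but the difference is on the safe side and does not affect this point.

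**2. STAI-II taken before the material, STAI-I level as outcome.** ANCOVA power uses λ = N f²/(1 − r²) with df 2 and 74. The pairwise half-width is t × √(2/26) unadjusted (75 df) and t × √(2/26) × √(1 − r²) × √(1 + 1/73) adjusted (74 df). Unadjusted at 95%: 1.992 × 0.2774 = 0.5525 SD.

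| | λ | Power, f = 0.40 | 95% half-width | Narrower by | 98.33% half-width |
|---|---|---|---|---|---|
| Unadjusted | 12.48 | 88.28% | 0.552 | – | 0.679 |
| r = 0 | 12.48 | 88.26% | 0.556 | −0.7% | 0.684 |
| r = 0.3 | 13.71 | 91.2% | 0.531 | 4% | 0.653 |
| r = 0.5 | 16.64 | 95.6% | 0.482 | 13% | 0.592 |
| r = 0.7 | 24.47 | 99.5% | 0.397 | 28% | 0.489 |

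The 98.33% level is 1 − 0.05/3, matching Bonferroni for three contrasts.

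**3. Measured trait imbalance, material without effect.** If one group's true trait mean is 0.5 SD higher, its STAI-I mean is 0.5r higher and λ = 26 × (2/3) × (0.5r)² = 0.39, 1.08, 2.12. ANOVA then rejects in 8%, 14% and 23% of studies at r = 0.3, 0.5, 0.7. In simulation (20,000 runs, 26 per group) ANCOVA rejects in 5% throughout.

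**4. STAI-II taken after the material and shifted by s SD in the video group.** The adjusted video effect moves by about −r·s. At s = 0.5 the simulated shifts are −0.149, −0.249 and −0.352, against −0.15, −0.25 and −0.35 by formula. With no true effect, ANCOVA rejects in:

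| s | r = 0.3 | r = 0.5 | r = 0.7 |
|---|---|---|---|
| 0.3 | 6% | 9% | 17% |
| 0.5 | 8% | 16% | 40% |

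ANOVA stays at 5%. With a true video effect of 0.5 SD and r = 0.5, ANOVA has 43% power. ANCOVA has 54% at s = 0, 36% (estimate 0.40 SD) at s = 0.2, and 29% (0.35 SD) at s = 0.3.

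**5. Change score as outcome.** With equal SDs, the share of variance explained by trait is (r₂ − r₁)²/(2 − 2c), where r₁ and r₂ are its correlations with STAI-I before and after biopsy. This is zero if r₁ = r₂. With r₁ = 0.3, r₂ = 0.5, c = 0.6 it is 0.04/0.8 = 0.05, and the half-width narrows by 1 − √0.95 = 2.5%.

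**The case against.** The strongest reply is that the benefit rests on a condition the plan does not meet. In the order listed, STAI-II follows the material, and then the unadjusted comparison already planned is the one to keep as primary. This stands, and it is why timing is part of the point.

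Second, reordering may be too late. Section 14 gives "End of patient recruitment: 30.12.2024" and the final Statistical Analysis text is in the past tense. The documents do not establish that collection is finished, so the fix has two branches.

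Third, the endpoint can naturally be read as a change, given the before-and-after wording and the paired tests in section 18. The 4% to 28% would then not apply. This also stands.

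Fourth, r is assumed, and the exclusions in section 9 (anxiety, depressive and panic disorders, PTSD, and high pre-procedure VAS) could restrict the trait range, so the upper end may be optimistic. The larger false-positive figures likewise need material that moves trait answers by 0.3 to 0.5 SD while leaving state anxiety alone. A 0.1 SD shift in the direction of the effect still leaves ANCOVA slightly ahead at r = 0.5 (45% against 43%).

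A reader might infer that the planned analysis is invalid or the study underpowered. Neither follows: the unadjusted test is valid if the groups are comparable, and power is 88% on the plan's own effect size. Nor do the documents rule adjustment out; they leave the role of STAI-II unstated.

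**Conclusion.** The point holds as a low-cost improvement and a gap in specification. STAI-II is collected in every group, no analysis is assigned to it, and its listed position after the material makes it unsafe as a covariate now.

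If it is taken before the material and a STAI-I level is the outcome, assumed correlations of 0.3 to 0.7 narrow pairwise intervals by about 4% to 28%, and a measured trait imbalance no longer enters the group effect. For a change score the gain is nil or small.

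It would be tempting to conclude that adding STAI-II to the model repairs the missing allocation method. It does not: unmeasured differences remain, and adjustment is no substitute for randomisation. Nor do the documents support adjusting for STAI-II in its present position without a stated assumption that the material left it unchanged.

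**What to change.** **If patients are still to be enrolled.** In section 4, Video Group and Image Group, place STAI-II directly after the VAS test and before the material; the control group already has it directly after VAS. In section 18 and the final Statistical Analysis text, name one primary analysis: ANCOVA of post-procedure STAI-I on group, adjusted for that STAI-II. Report the three adjusted pairwise differences with Bonferroni-adjusted p-values and matching 98.33% intervals. Show the unadjusted ANOVA or Kruskal-Wallis result alongside, which also serves as the check if residuals are clearly non-normal. Do not adjust for pre-procedure STAI-I as now timed, since it too follows the material.

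**If STAI-II was already collected after the material.** Keep the unadjusted comparison primary. Report the adjusted result only as a sensitivity analysis, stating that it assumes the material did not change STAI-II answers and that otherwise the group effect moves by about −r·s.

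**In either case,** reconcile section 11 with section 4 on whether STAI-II is repeated after biopsy.

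**Cost.** Plan wording and, in the first case, moving one questionnaire; there is no new measurement and the model runs in SPSS. If r were zero, the lost degree of freedom takes power from 88.28% to 88.26% at f = 0.40. In simulation, which also counts chance covariate imbalance, the loss is about 0.4 to 0.6 of a percentage point. One drawback remains: STAI-II would be given apart from STAI-I in the video and image groups but together with it in the control group. In the second case the cost is wording and one extra analysis.

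### No baseline-adjusted analysis of VAS pain is specified, although every group has a VAS listed before any visual material and another after biopsy

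*Combined protocol and SAP*

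**What the plan says.** Section 4 introduces the design thus: "This is a comparative study of anxiety scores and visual analog scale (VAS) pain scores before and after the procedure". In the control, video and image groups alike, the first step after verbal information is "VAS test is applied". In the video group the next step is "Videos about the procedure are found and watched with the patients via digital video platforms"; in the image group it is "Illustrated drawings (from books) about the procedure are shown to the patients". All three groups end with "After biopsy: VAS and STAI-I are re-administered".

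On analysis, the final Statistical Analysis section says "Group comparisons were made using the Kruskal-Wallis test for non-parametric data and ANOVA for normally distributed data", followed by "Post-hoc pairwise comparisons were conducted using the Mann-Whitney U test with Bonferroni correction". It names no covariate and does not mention VAS. Section 18 opens a list of nine methods with "Both parametric tests (t-test, ANOVA, Pearson correlation, linear regression", but ties none of them to an outcome, covariate or model.

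Section 17 makes STAI the primary endpoint. Section 9 excludes patients whose pre-procedure VAS is 5 or more. No section describes how patients are allocated to groups.

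**The concern.** The first VAS precedes the video or drawings, so the visual material cannot have affected it, and it can serve as a baseline covariate for post-biopsy pain. The named group tests do not use it.

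Two things follow. If post-biopsy VAS is compared as it stands, some precision may be lost, and a difference between groups in first VAS passes partly into the result. This matters more than usual because no allocation method is described. If change in VAS is compared instead, as the before-and-after description in section 4 might suggest, precision can be worse still. As nothing fixes the test variable, the choice stays open until the data are seen. Pain is one of the two outcomes in the title.

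**Working it through.** **Inputs from the documents.** Three groups; f = 0.40; alpha 0.05; power 80%; 26 per group, 78 in total (section 7 and the final Statistical Analysis section).

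**Assumptions.** The documents give neither the pre/post VAS correlation (rho) nor the ratio k = SD pre / SD post. I take rho = 0, 0.3 and 0.5, and k = 1, 0.75 and 0.5. The documents tie f = 0.40 to no outcome, so applying it to post-biopsy VAS is a further assumption.

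**Step 1: the plan's own figure.** One-way ANOVA, noncentral F with df 2 and N − 3, noncentrality N × f². Power of 80% needs N = 64 (0.805), or 66 with equal groups (0.818). At N = 78 the noncentrality is 78 × 0.16 = 12.48 and power is 0.883. So 78 does not reproduce as a three-group ANOVA at 80% power. It errs on the large side, and this does not bear on the present point. The 0.883 is the benchmark for an unadjusted post-biopsy comparison.

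**Step 2: variance relative to the unadjusted post-biopsy score.**
- ANCOVA: 1 − rho², with one error df fewer (74 instead of 75).
- Change score: 1 + k² − 2 × rho × k, which is 2(1 − rho) when k = 1.

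**Step 3: ANCOVA against the unadjusted post-biopsy score.** Noncentrality is 12.48/(1 − rho²).

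| rho | Relative variance | Noncentrality | Power, ANCOVA | Power, unadjusted |
|---|---|---|---|---|
| 0 | 1.00 | 12.48 | 0.8826 | 0.8828 |
| 0.3 | 0.91 | 13.71 | 0.912 | 0.883 |
| 0.5 | 0.75 | 16.64 | 0.956 | 0.883 |

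At f = 0.30 the unadjusted power is 0.638, against 0.682 (rho 0.3) and 0.770 (rho 0.5) with ANCOVA. A simulation of 4000 runs per rho at f = 0.40 gave ANCOVA power of 0.876, 0.905 and 0.954 for rho 0, 0.3 and 0.5, and unadjusted power of 0.880 to 0.882.

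**Step 4: change score against ANCOVA.** The extra patients needed are the variance ratio minus 1.

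| k | rho 0.3 | rho 0.5 |
|---|---|---|
| 1 | 1.40/0.91 = 1.54, 54% more | 1.00/0.75 = 1.33, 33% more |
| 0.75 | 1.1125/0.91 = 1.22, 22% more | 0.8125/0.75 = 1.08, 8% more |
| 0.5 | 0.95/0.91 = 1.04, 4% more | 0.75/0.75 = 1.00, 0% more |

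At f = 0.40 and rho 0.3, change-score power is 0.749 for k = 1 and 0.899 for k = 0.5, against 0.912 for ANCOVA.

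**Step 5: effect of the VAS exclusion.** If u is the ratio of restricted to unrestricted baseline SD, the correlation becomes rho × u / √(1 − rho² + rho² × u²). As an illustration, assumed baseline means of 1.5 to 4 and SDs of 1.5 to 2, cut at 5, give u from 0.66 to 0.95. A rho of 0.3 then falls to about 0.20–0.29, and the variance saving over the unadjusted score is about 4–8%. A rho of 0.5 falls to about 0.36–0.48, a saving of about 13–23%.

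**Step 6: baseline imbalance.** A 1-point difference in mean first VAS shifts the unadjusted post-biopsy difference by rho/k points: 0.3 to 0.5 if k = 1, and 0.3/0.5 = 0.6 to 0.5/0.5 = 1.0 if k = 0.5.

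**The case against.** Four objections have force.

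**The plan does not commit to an unadjusted or a change-score analysis of VAS.** A reader might infer either one: the first from the tests named in the final section, the second from the before-and-after sentence in section 4. The documents support neither as a fixed choice. The final section never mentions VAS, the section 4 sentence is descriptive, and linear regression in section 18 could hold a baseline adjustment. What stands is that none is specified; an unassigned entry in a list of nine methods does not do that.

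**The large figures belong to a plan the documents never adopt.** The 54% and 33%, and power of 75% against 91%, compare ANCOVA with a change score and require equal SDs. First VAS is capped below 5 and post-biopsy VAS is not, so a smaller pre SD is plausible, and the excess then shrinks towards 4% and 0%. A reader might also think the cap strengthens the case against a change score. It does the reverse: with equal SDs before truncation, simulation under assumed baselines (mean 2–4, SD 1.5–2) moved the change/ANCOVA variance ratio from 1.54 to 1.26–1.48 at rho 0.3, and from 1.33 to 1.16–1.30 at rho 0.5.

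**Adjustment does not make the groups comparable.** It deals with linear imbalance in one measured score. Section 9 reads a high pre-procedure VAS as a sign of an anxiety-stress disorder, so this score may not measure quite what post-biopsy VAS measures. It is still a usable covariate, but its correlation with biopsy pain may be low.

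**Pain is not the primary endpoint.** This is correct, and it limits the weight of the point.

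**Conclusion.** The point holds in a limited form: a VAS that precedes the visual material is collected in every group, and no analysis that adjusts for it is specified. ANCOVA is a low-risk improvement whatever the correlation, since at rho = 0 it costs 0.0002 in power. Against an unadjusted post-biopsy comparison at f = 0.40, the gain is nil at rho 0, about 3 percentage points at 0.3 and about 7 at 0.5, and probably less once the VAS exclusion is allowed for. Against a change score it runs from 54% to 0% over the assumed rho of 0.3–0.5 and SD ratios of 0.5–1.

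These sizes rest on assumed rho and k, a linear relation, and f = 0.40 applied to VAS. Other imbalance between the groups remains.

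A reader might infer that the same remedy serves the STAI. It does not: in the video and image groups the pre-procedure STAI-I is listed after the visual material, so it is not a pre-exposure baseline. The point therefore improves the analysis of a non-primary outcome and closes an open choice; it does not affect the primary endpoint.

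**What to change.** Add to the final Statistical Analysis section, before the data are analysed, wording to this effect:

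*Post-biopsy VAS will be compared among the three groups by ANCOVA, with the VAS taken before the visual material as covariate. Adjusted differences for video minus verbal-only and image minus verbal-only will be reported with Bonferroni-corrected 95% confidence intervals. If residuals are clearly non-normal, a rank-based ANCOVA will be used as a check. Change in VAS will not be the test variable.*

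The Bonferroni correction keeps to what is already planned for pairwise comparisons. The report should say that adjustment covers first VAS only, and how patients came to be in each group.

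Cost: one sentence or so of plan text and one degree of freedom. Both VAS scores are already collected in all three groups.
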